#### **9.3.2. Analysis Methods**

For the EQ-5D descriptive system, descriptive statistics on the actual value and change from baseline will be presented by analysis phase and by cohort.

For the EQ-5D VAS and for the Valuation index, descriptive statistics for the actual and change from baseline values at each time point will be displayed. In addition, mean changes from baseline will be explored as appropriate for different subgroups: participants with HBsAg seroclearance 24 weeks and 48 weeks after completion of consolidation phase treatment, in patients stopping NA

(at FU Week 2) without restarting NA treatment, versus those without HBsAg seroclearance at those time points.

The clinically important thresholds of 7 and 10 will be used to interpret the mean change from baseline in the VAS.

The number (and percentage) of participants with clinically important improvement/ worsening will be presented for EQ-5D VAS:

- Clinical Important Improvement = change from baseline  $\geq 7$ , and also for  $\geq 10$
- Clinical Important Worsening = change from baseline  $\leq -7$ , and also for  $\leq -10$ .
- Other changes from baseline values are categorized as ‘No Clinically Important Change’.

A cumulative distribution function of the EQ-5D VAS will be drawn at different time points (baseline and changes from baseline).

## **9.4. Patient Global Impression of Change Scale (PGIC)**

### **9.4.1. Definition**

The PGIC scale is a single-item PRO scale aimed at assessing the participant’s perceptions of change (improvement or worsening) in how they feel overall compared to the beginning of the study. Response options include: “Much better”, “Better”, “A little better”, “No change”, “A little worse”, “Worse”, “Much worse”.

### **9.4.2. Analysis Methods**

The tabulation of the number and percentage of participants at each response level will be displayed per time point by analysis phase and by cohort.

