## Patient Global Impression of Change Scale, Version 1.0

The PGIC scale is a single-item PRO scale aimed at assessing the participant's perceptions of change (improvement or worsening) in how they feel overall compared to the beginning of the study. Response options include: "Much better", "Better", "A little better", "No change", "A little worse", "Worse", "Much worse". It takes less than a minute to complete the scale. The PGIC responses will be used as anchors to perform responder analyses and to evaluate the ability to detect change for the HBQOL and the HBV-specific self-stigma PRO scale.

The PGIC scale version 1 is provided in Section 10.13, Appendix 13, Patient Global Impression of Change Scale.

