# 9.4.1.4. Patient-reported Outcomes

The PRO scores will be analyzed descriptively as mean scores over time, and (if applicable) evaluated based on the proportion of participants experiencing a clinically important improvement or worsening in PRO scores from baseline during study intervention and follow-up. Analyses will also be performed on PRO score changes from baseline at specific time points (Week 24, end of consolidation phase, end of induction phase, FU Week 24, and FU Week 48 [EOS]), and between end of the consolidation phase and FU Week 48 (EOS) for different subgroups: participants with

HBsAg seroclearance 24 weeks and 48 weeks after completion of consolidation phase treatment, in patients stopping NA (at FU Week 2) without restarting NA treatment, versus those without HBsAg seroclearance at those time points.

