### Amendment 4:

Overall rationale of this Amendment:

This administrative amendment incorporates additional clarifications on subgroups and analyses which have been documented in the Data Presentation Specification.

Clarifications, Additions, Corrections		
Section Number and Name	Description of Change	Rationale
2.5.1 Subgroup for Efficacy Analyses	
Addition of the following subgroups:
 
 
- Immune tolerant
 
- Peg-responder definition #1
 
- Peg-responder definition #2
 
 
Removal of the following subgroups:
 
 
- NA treatment history
 
- Fibrosis stage
 
- Sex
 
- Geographical region
 
- Duration of exposure to antigens
 
 
Regrouping of the age categories: >30 years - ≤45 years, >45 years - ≤55 years in one category: >30 years
	To allow for a more focused assessment of factors impacting efficacy outcomes and reduce the overall number of outputs
5.4.1.3.1. Association Between Baseline Characteristics/Viral Blood Markers and Selected Efficacy Variables	Removal of the correlation analyses between off-treatment HBV markers and other endpoints	Insufficient data for correlation analysis since there is only one patient who has met the NA treatment completion criteria and stopped NA (i.e. off-treatment) at CW12.
5.4.1.3.1. Association between several endpoints	The title has been changed to reflect the analyses detailed in this subsection.	To characterize association between changes in viral and safety markers during PegIFN administration.

Clarifications, Additions, Corrections		
Section Number and Name	Description of Change	Rationale

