### 9.1.2. Analysis Methods

Descriptive statistics of the actual values and change from baseline values at each timepoint (including baseline, Week 24, end of induction, end of consolidation phase, FU Week 24 and FU Week48) for the derived scores will be displayed for subscales/domains and global score by analysis phase and by cohort. The proportion of participants experiencing a clinically important improvement or worsening from baseline (if applicable) at each timepoint will be calculated by analysis phase and by cohort. Clinically important improvement = change from baseline  $\geq 10$ , Clinically important worsening = change from baseline  $\leq -10$ . Other change from baseline values will be categorized as 'No clinically important change'. Analyses will also be performed on the changes from baseline at specific time points (end of consolidation phase, FU Week 24 and FU Week 48) as appropriate for different subgroups: participants with HBsAg seroclearance 24 weeks and 48 weeks after completion of consolidation phase treatment, in patients stopping NA (at FU Week 2) without restarting NA treatment, versus those without HBsAg seroclearance at those time points.

## 9.2. Short Form 36 version 2

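### The SAP omits the protocol's PGIC-anchored HBQOL analysis and its end-of-consolidation to FU Week 48 change, and its HBQOL response cut is unsourced and has the wrong sign

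*SAP*

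**What the plan says.** Protocol 8.1.2, on the PGIC: "The PGIC responses will be used as anchors to perform responder analyses and to evaluate the ability to detect change for the HBQOL". The commitment is unconditional. Protocol 9.4.1.4, repeated in the synopsis, plans PRO changes from baseline and also changes "between end of the consolidation phase and FU Week 48 (EOS) for different subgroups". Those subgroups are participants with HBsAg seroclearance who stopped NA and did not restart it, against participants without seroclearance.

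SAP 9.4.2 gives the whole PGIC analysis as: "The tabulation of the number and percentage of participants at each response level will be displayed per time point", split by phase and cohort. No SAP section links PGIC to HBQOL, and the instrument list opening SAP 9 leaves PGIC out.

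SAP 9.1.2 shows HBQOL values and changes from baseline at each visit. Its subgroup analysis reads: "Analyses will also be performed on the changes from baseline at specific time points (end of consolidation phase, FU Week 24 and FU Week 48". SAP 9.2.2 (SF-36) and 9.3.2 (EQ-5D) also give changes from baseline only, and SAP 2.2.1 makes study baseline the reference in every phase. For HBQOL response, SAP 9.1.2 sets "Clinically important improvement = change from baseline" of at least +10, and worsening as a change of -10 or lower.

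The Amendment 4 entry in the SAP history says that "there is only one patient who has met the NA treatment completion criteria and stopped NA".

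**The concern.** Two analyses that the protocol promises do not reach the SAP. The parts of the SAP amendment history available to this review give no reason, although Amendments 2 and 4 do list and explain other removals.

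Two things are lost. First, the HBQOL responder proportions have no link to what participants say has changed, because the only planned link was the PGIC. Secondly, no within-participant estimate is planned of how quality of life moves once JNJ-3989 and PegIFN-α2a stop. The SAP already has the device it needs: SAP 5.3.2.2.1 plans change from a consolidation reference point for HBsAg, HBeAg, HBV DNA and ALT. It was not extended to the PROs.

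The sign of the cut matters more for a reader of the tables. Followed as written, it reports participants who got worse as improved, and the reverse.

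**Working it through.** The plan states no design figure on this point. The one PRO calculation it shows, the HBQOL example in SAP 9.1.1, reproduces: (25 + 75 + 50)/3 = 50.

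**Direction of the cut.** Protocol 8.1.2 and SAP 9.1.1 both score HBQOL from 0 (best) to 100 (worst). Wherever the SAP defines change from baseline (for example SAP 5.3.1.2.1), it is the later value minus baseline. Then:
- 20 to 45: change = 45 - 20 = +25. Quality of life is worse; SAP 9.1.2 labels it improvement.
- 45 to 20: change = 20 - 45 = -25. Quality of life is better; SAP 9.1.2 labels it worsening.

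SAP 9.2.2 and 9.3.2 use the same sign rule for SF-36 and the EQ-5D VAS. It is right there because higher is better on those scales.

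**Source of the cut.** The protocol states no 10-point threshold. SAP 9.1.2 cites nothing for it, and the SAP reference list has no HBQOL or PGIC paper.

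**What the cut requires.** One item moving one level is worth 25 points (SAP 9.1.1), and a score is the mean of its items. So the step is 25/n, the steps needed are 10/(25/n) rounded up, and the smallest qualifying change is steps × 25/n.

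| Items in score | Step | Steps needed | Smallest change of at least 10 |
|---|---|---|---|
| 3 | 8.33 | 2 | 16.67 |
| 4 | 6.25 | 2 | 12.5 |
| 5 | 5.00 | 2 | 10.0 |
| 6 | 4.17 | 3 | 12.5 |
| 8 | 3.13 | 4 | 12.5 |
| 31 (global) | 0.81 | 13 | 10.48 |

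**Availability of visits.** The Schedule of Activities places HBQOL and PGIC together at Week 24, end of induction, consolidation Week 12, FU Week 24 and FU Week 48. No new collection is needed for either analysis.

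**Precision of the paired change.** Half-width of the 90% CI = t(0.95, n-1) × SD × √(2(1-ρ))/√n. Take n = 30, from SAP 1.4 (33 less 10% dropout), so t(0.95, 29) = 1.699. The documents give neither SD nor the between-visit correlation ρ; both are assumptions.
- SD 20, ρ = 0.5: 1.699 × 20 × 1.000/5.477 = 6.2 points.
- SD 20, ρ = 0: 1.699 × 20 × 1.414/5.477 = 8.8 points. This is what a reader would get by treating the two visits' tabulated SDs as independent.
- SD 10 to 25 with ρ 0.3 to 0.9: from 1.4 to 9.2 points.

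**Size of the retained subgroup.** The NA completion criteria require HBsAg <10 IU/mL (Protocol 6.6.1), whereas seroclearance means HBsAg below 0.05 IU/mL (SAP 5.1.2 and 5.3.1.1.3). One participant met the criteria and stopped NA. The seroclearance-off-NA group therefore has at most one member, and possibly none.

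**The case against.** The strongest reply is that little is lost. The PROs are exploratory and descriptive, and Protocol 9.4.1.4 hedges the clinically important change analysis with a proviso that it be applicable. SAP 9.1.2, 9.2.2 and 9.3.2 report values at both visits, so the mean shift can be read off. The protocol frames the post-consolidation change by seroclearance off NA, and that contrast is now empty or nearly so. The PGIC sentence also names a self-stigma scale that is not among the four instruments, which suggests carried-over text. A seven-level PGIC in about 60 participants will leave small categories, and a cut estimated and applied in the same data is weak. The Data Presentation Specification, which the SAP history cites, was not available and may hold more detail.

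Much of this stands and limits the point. A reader might infer that the SAP leaves the post-treatment course unestimated. It does not: only the paired change and its precision are missing, although the difference of the two tabulated means equals the paired mean only if the same participants contribute to both. A reader might also infer that the contrast would show recovery off treatment, or recovery from PegIFN-α2a. JNJ-3989 stops with PegIFN-α2a, and participants who do not meet the completion criteria continue NA through follow-up, so neither reading is supported. Nor do the documents say that the one participant who stopped NA had seroclearance.

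The table above does not show that the cut means something radically different on each score. The differences are mostly rounding of one 10-point cut on short scales. No PRO completion rates are given, so how many participants would contribute is unknown.

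None of this accounts for the missing anchor analysis, the missing source or the reversed sign.

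**Conclusion.** The point holds as a minor departure of the SAP from the protocol, with one outright error beside it. The PGIC anchor and the end-of-consolidation to FU Week 48 change are in the protocol and absent from the SAP, with no recorded reason in the material available. The HBQOL cut is unsourced, and its direction contradicts the SAP's own scoring. That conclusion assumes change means later value minus baseline, as elsewhere in the SAP.

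The loss is precision and interpretability in exploratory outcomes: a paired estimate with a half-width of about 6 points under the stated assumptions, and responder proportions with no link to participants' own rating. The primary endpoint and the sample size are unaffected. The documents do not support making PGIC-derived thresholds the main HBQOL cut; a supportive role is as far as the likely category sizes allow.

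**What to change.** 1. In SAP 9.1.2, 9.2.2 and 9.3.2, add the paired change from end of consolidation to FU Week 48 for HBQOL, SF-36 and EQ-5D, by cohort, with a two-sided 90% CI (the level in SAP 5.1.1) and the number contributing to both visits. This extends the protocol's subgroup framing, and the SAP should say so. List individually any participant with seroclearance off NA instead of treating that participant as a comparison group. Describe the result as change after JNJ-3989 and PegIFN-α2a stop, with NA continuing in nearly all participants.

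2. In SAP 9.1.2 and 9.4.2, add a descriptive summary of HBQOL change from baseline by same-visit PGIC category, as a supportive anchor analysis. Change from baseline is the matching quantity because the PGIC asks about change since the start of the study. Keep the fixed cut, and note that PGIC categories will be small. Add PGIC to the instrument list in SAP 9.

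3. In SAP 9.1.2, correct the direction of the HBQOL cut: improvement is a change of -10 or lower, worsening a change of +10 or higher. State its source, or say that it is a convention.

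If either omitted analysis was dropped on purpose, record the reason in the amendment history.

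The cost is SAP wording and a few extra tables, with no new data. The drawback is that anchor values from small PGIC categories will be imprecise.

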## ATTACHMENT 1: SELECTED MAJOR PROTOCOL DEVIATIONS FOR ANALYSIS PURPOSES

The major protocol deviations that may affect the assessment of efficacy will be updated to reflect protocol amendment and be finalized prior to the primary analysis database lock. The major deviations that are selected to exclude participants from the PP set are listed below.

Sequence No.	Protocol Deviation Description (DVTERM)	Protocol Deviation Coded Term (DVDECOD)	Exclude from PP
1	Inclusion criterion A01(M01) not met:  Participant was <specify> years old.	Entered but did not satisfy criteria	Yes
1.1	Inclusion criterion A01.1(M01) not met:  Participant was <specify participant's age> years old.	Entered but did not satisfy criteria	Yes
2	Inclusion criterion M02 not met:  a) Participant didn't have PE, medical review, vital signs and 12-lead ECG performed at screening; b) The abnormalities found on the basis of PE, medical review, vital signs and 12-lead ECG performed at screening, are not consistent with the underlying illness in the study population.	Entered but did not satisfy criteria	No
3	Inclusion criterion A03 (M03d) not met:  Chronic HBeAg positive HBV infection was not documented by HBsAg positivity at screening and/or chronicity was not documented by serum HBsAg positivity, HBeAg positivity or HBV DNA positivity documented transition event., or by alternative markers of chronicity.  Inclusion criterion 3 not met: participant a) was not treatment naïve b) was not HBeAg positive c) did not have serum HBV DNA at screening $\geq 20,000$ IU/mL or d) did not have ALT $\leq 2x$ ULN at screening and at least once $> 6$ months prior to screening.	Entered but did not satisfy criteria	Yes
3.1	Inclusion criterion A03 1 (M03d) not met:  Chronic HBeAg positive HBV infection was not documented by HBsAg positivity at screening and/or chronicity was not documented by serum HBsAg positivity, HBeAg positivity or HBV DNA positivity documented transition event., or by alternative markers of chronicity.  Inclusion criterion 3 not met. a) Participant is currently treated (defined as having received $< 9$ months of NA treatment $\geq 12$ months prior to screening) including treatment-naïve participants b) was not HBeAg positive c) did not have serum HBV DNA at screening $\geq 20,000$ IU/mL or d) did not have normal ALT at screening and at least once $> 6$ months prior to screening.	Entered but did not satisfy criteria	Yes
3.2	Inclusion criterion A03 2 (M03d) not met:  Chronic HBeAg positive HBV infection was not documented by HBsAg positivity at screening and/or chronicity was not documented by serum HBsAg positivity, HBeAg positivity or HBV DNA positivity documented transition event., or by alternative markers of chronicity.  Inclusion criterion 3 not met. a) Participant is currently treated (defined as having received $< 9$ months of NA treatment $\geq 12$ months prior to screening) including treatment-naïve participants b) was not HBeAg positive c) did not have serum HBV DNA at screening $\geq 20,000$ IU/mL or d) did not have ALT $< 2x$ ULN at screening and at least once $> 6$ months prior to screening.	Entered but did not satisfy criteria	Yes
4	Inclusion criterion M04 not met:	Entered but did not satisfy criteria	No

Sequence No.	Protocol Deviation Description (DVTERM)	Protocol Deviation Coded Term (DVDECOD)	Exclude from PP
5	Participant has a BMI >35.0 kg/ m  or <18.0 kg/ m  . Inclusion A05 (M05) not met: Participant (or legally acceptable representative) did not provide consent to participate in the study.	Entered but did not satisfy criteria	Yes
6	Inclusion criterion M06 not met: Participant provided an optional DNA sample which was analyzed; however, she/he did not sign a separate ICF.	Entered but did not satisfy criteria	No in general, but Yes for the Optional DNA (Pharmacogenomics DNA) sample data
7	Inclusion criterion A07 (M07) not met: Participant does not agree to remain on a highly effective method while receiving study intervention and until 90 days after last dose.	Entered but did not satisfy criteria	No
13	Inclusion criterion A13 not met: Participant does not have < specify the missing data> a. Fibroscan liver stiffness measurement =<9.0 kPa within 6 months prior to screening or at the time of screening b. and a liver biopsy result classified as Metavir F0-F2 within 1 year prior to screening or at the time of screening.	Entered but did not satisfy criteria	Yes
14	Inclusion criterion A14 not met: Participant participated in the PK sub study, but she/he did not sign a separate ICF.	Entered but did not satisfy criteria	No I
15	Exclusion criterion A01 (M01) met: Participant has evidence of <specify the infection: hepatitis A virus infection (hepatitis A antibody IgM), HCV infection (HCV antibody), hepatitis D virus (HDV) infection (HDV antibody), hepatitis E virus (HEV) infection (hepatitis E antibody IgM), or HIV-1 or HIV-2 infection (confirmed by antibodies)> at screening.	Entered but did not satisfy criteria	Yes
15.1	Exclusion criterion A01.1 (M01) met: Participant has evidence of <specify the infection hepatitis A virus infection (hepatitis A antibody IgM), HCV infection (HCV antibody), hepatitis D virus (HDV) infection (HDV antibody), hepatitis E virus (HEV) infection (hepatitis E antibody IgM), or HIV-1 or HIV-2 infection (confirmed by antibodies)> at screening (and no negative HIV RNA test).	Entered but did not satisfy criteria	Yes
15.2	Exclusion criterion A01.2 (M01) met: Participant has evidence of <specify the infection hepatitis A virus infection (hepatitis A antibody IgM), HCV infection (HCV antibody), hepatitis D virus (HDV) infection (HDV antibody), hepatitis E virus (HEV) infection (hepatitis E antibody IgM), or HIV-1 or HIV-2 infection (confirmed by antibodies)> at screening (and no negative HIV RNA test).  Patients confirmed with HIV-1 or HIV-2 infection on antiretroviral treatment.	Entered but did not satisfy criteria	Yes
16	Exclusion criterion M02.1 met: Participant has evidence of hepatic decompensation at any time point prior to or at the time of screening: a. Total bilirubin >1.5xULN a , OR b. Direct bilirubin >1.2xULN a , OR c. Prothrombin time >1.3xULN a (unless caused by anticoagulation therapy or vitamin K deficiency), OR d. Serum albumin <3.2 g/dL a , OR e. History of clinical symptoms of hepatic decompensation (e.g., ascites, jaundice, hepatic encephalopathy or coagulopathy, especially if resulting in a Child-Pugh classification B or C at the time clinical symptoms present or at screening). a Not explained by anything other than hepatic decompensation.	Entered but did not satisfy criteria	Yes
17	Exclusion Criterion M03 met: Participant has a history or evidence of hepatic decompensation, including but not limited to: portal hypertension, ascites, hepatic encephalopathy, esophageal varices. <Specify>.	Entered but did not satisfy criteria	Yes
18	Exclusions Criterion M04 met:	Entered but did not satisfy criteria	Yes

Sequence No.	Protocol Deviation Description (DVTERM)	Protocol Deviation Coded Term (DVDECOD)	Exclude from PP
	Participants with evidence of liver disease of non-HBV etiology. This includes but is not limited to hepatitis infections mentioned in exclusion criterion A01, drug- or alcohol-related liver disease, autoimmune hepatitis, hemochromatosis, Wilson's disease, $\alpha$ -1 antitrypsin deficiency, primary biliary cholangitis, primary sclerosing cholangitis, Gilbert's syndrome (mild cases are allowed, see exclusion criterion A02a) or any other non-HBV liver disease considered clinically significant by the investigator. <specify>.		
19	Exclusion Criterion M05 met:  Participant with signs of HCC or clinically relevant renal abnormalities on an abdominal ultrasound performed within 6 months prior to screening or at the time of screening. The Participant is included if HCC / abnormal ultrasound results have been ruled out.	Entered but did not satisfy criteria	Yes
20	Exclusion Criterion A06 (M06) met:  Participant has one or more of the following laboratory abnormalities at screening as defined by the Division of Acquired Immunodeficiency Syndrome (DAIDS) Toxicity Grading Scale 
 
a. Estimated glomerular filtration rate (e.g. FR) <80 mL/min/1.73 m^2 at screening, calculated by the Chronic Kidney Disease Epidemiology Collaboration (CKD-EPI) formula;
 
b. Pancreatic lipase elevation <math>\geq</math>grade 3;
 
c. Pancreatic amylase elevation <math>\geq</math>grade 3;
 
d. Hemoglobin <math>\leq</math>10.9 g/dL (males), <math>\leq</math>10.4 g/dL (females);
 
e. Platelet count <math>\leq</math>lower limit of normal (LLN);
 
f. Alpha-fetoprotein >100 ng/mL;
 
g. Any other laboratory abnormality considered to be clinically significant by the investigator (also see inclusion criterion A03).
 
	Entered but did not satisfy criteria	No
21	Exclusion Criterion M07 met: Participant has hemoglobin A1c value >8% <specify value> at screening.	Entered but did not satisfy criteria	No
22	Exclusion criterion M08 met:  Participant has a history of malignancy within <specify number of years> years before screening.	Entered but did not satisfy criteria	No
23	Exclusion criterion M09.1 met:  Participant has an abnormal sinus rhythm (heart rate <45 or >100 beats per minute [bpm]); QT interval corrected for heart rate according to Fridericia's formula (QTcF) >450 ms for males and >470 ms for females; QRS interval $\geq$ 120 ms; PR interval >220 ms; abnormal conduction; or any other clinically significant abnormalities on a 12-lead ECG at screening. <Specify details>.	Entered but did not satisfy criteria	No
24	Exclusion Criterion M10 met:  Participant has a history of or current cardiac arrhythmias (e.g., extrasystole, tachycardia at rest), history of risk factors for Torsade de Pointes syndrome (e.g., hypokalemia, family history of long QT Syndrome) or history or other clinical evidence of significant or unstable cardiac disease (e.g., angina, congestive heart failure, myocardial infarction, diastolic dysfunction, significant arrhythmia and/or coronary heart disease), moderate to severe valvular disease, or uncontrolled hypertension at screening. <specify significant, unstable cardiac disease, moderate to severe valvular disease or uncontrolled hypertension> at screening.	Entered but did not satisfy criteria	No
25	Exclusion Criterion M11 met:  Participant has a current or previous illness for which, in the opinion of the investigator and/or sponsor, participation would not be in the best interest of the participant<current or previous> illness that might interfere with the study. <specify illness>.	Entered but did not satisfy criteria	No
26	Exclusion Criterion M12 met:  Participant received an organ transplant (except for skin, hair, or cornea transplants) <specify details>.	Entered but did not satisfy criteria	No
27	Exclusion Criterion M13 met:  Participant has a history of clinically significant skin disease requiring regular or periodic treatment. <specify skin disease>.	Entered but did not satisfy criteria	No

Sequence No.	Protocol Deviation Description (DVTERM)	Protocol Deviation Coded Term (DVDECOD)	Exclude from PP
28	Exclusion Criterion M14 met  Participant has a history of clinically relevant alcohol or drug abuse within 12 months of screening.	Entered but did not satisfy criteria	No
29	Exclusion Criterion M15 met:  Participant has a history of clinically relevant drug rash: <specify drug rash>.	Entered but did not satisfy criteria	No
30	Exclusion Criterion A16 (M16) met:  Participant has taken a disallowed therapy before the planned first dose of study intervention as noted in Section 6.5 of the Protocol, Concomitant Therapy before the planned first dose of study intervention.: <specify disallowed therapy>.	Entered but did not satisfy criteria	If classified as major protocol deviation, excluded from PP set.
31	Exclusion Criterion M17 met:  Participant received <invasive investigational medical device within 3 months> Or received an investigational intervention or a biological product, immunoglobulin or other blood product not intended for the treatment of HBV within 6 months or 5 half-lives (whichever is longer), before the planned first dose of study intervention, Or is currently enrolled in an interventional clinical study with an investigational product.	Entered but did not satisfy criteria	If classified as major protocol deviation, excluded from PP set.
32	Exclusion Criterion A18 (M18) met:  Participant is <pregnant, breast-feeding or planning to become pregnant> while on study treatment or within 90 days after the last dose.	Entered but did not satisfy criteria	No
33	Exclusion Criterion A19 (M19) met:  Male Participant is planning to father a child while enrolled in this study or within 90 days after the last dose of JNJ-3989 and JNJ-6379.	Entered but did not satisfy criteria	No
34	Exclusion Criterion M20 met:  Participant had major surgery within 12 weeks before screening, has not fully recovered of surgery or planned surgery: <specify surgery and date>.	Entered but did not satisfy criteria	No
35	Exclusion Criterion M21 met:  Participant is an employee of the investigator or study site, with direct involvement in the proposed study or other studies under the direction of that investigator or study site, as well as family members of the employees or the investigator <specify the investigator or study site>.	Entered but did not satisfy criteria	No
36	Exclusion Criterion M22.1 met:  Participant is vulnerable.	Entered but did not satisfy criteria	Yes
37	Exclusion Criterion A23 met:  Participant has a known <specify allergy, hypersensitivity or intolerance to JnJ-3989 or JnJ-6379 or their excipients>.	Entered but did not satisfy criteria	No
37.1	Exclusion Criterion A23.1 met:  Participant has a known <specify allergy, hypersensitivity or intolerance to JnJ-3989 or its excipients>.	Entered but did not satisfy criteria	No
38	Exclusion Criterion A24 met:  Participant has a known contraindication to the use of tenofovir disoproxil <provide details>.	Entered but did not satisfy criteria	No
39	Exclusion Criterion A25 met:  Participants has a contraindication to the use of PegIFN- $\alpha$ 2a as per prescribing information <provide details>	Entered but did not satisfy criteria	No
39.1	Exclusion Criterion A25.1 met:  Participant has a contraindication to the use of PegIFN- $\alpha$ 2a as per prescribing information <provide details>.	Entered but did not satisfy criteria	No
39.2	Exclusion Criterion A25.2 met:  Participants has a contraindication to the use of PegIFN- $\alpha$ 2a as per prescribing information <provide details>.	Entered but did not satisfy criteria	No
39.3	Exclusion Criterion A25.4 met:	Entered but did not satisfy criteria	No

Sequence No.	Protocol Deviation Description (DVTERM)	Protocol Deviation Coded Term (DVDECOD)	Exclude from PP
	Participants has a contraindication to the use of PegIFN- $\alpha$ 2a as per prescribing information <provide details>.		
40	Participant used disallowed medication (i.e., HBV antiviral medicines as defined in description of this criterion) from 12 months prior to screening until end of follow-up: <specify treatment, dose, unit, frequency, reason administered>.	Received a disallowed concomitant treatment	If classified as major protocol deviation, excluded from PP set.
41	Participant used disallowed medication (as defined in description of this criterion) from 6 months prior to baseline until end of follow-up: <specify treatment, dose, unit, frequency, reason administered>.	Received a disallowed concomitant treatment	If classified as major protocol deviation, excluded from PP set.
42	Participant used disallowed medication (i.e., any investigational agent other than the study intervention taken in the context of this study) from 6 months prior to screening until end of follow-up: <specify treatment, dose, unit, frequency, reason administered>.	Received a disallowed concomitant treatment	If classified as major protocol deviation, excluded from PP set.
42.1	Participant used disallowed medication (i.e., any investigational agent other than the study intervention taken in the context of this study) from 6 months prior to screening until end of follow-up: <specify treatment, dose, unit, frequency, reason administered>.	Received a disallowed concomitant treatment	If classified as major protocol deviation, excluded from PP set.
43	Participant used disallowed medication (as defined in description of this criterion) from screening until end of follow-up: <specify treatment, dose, unit, frequency, reason administered>.	Received a disallowed concomitant treatment	If classified as major protocol deviation, excluded from PP set.
43.1	Participant used disallowed inhibitor/medication (as defined in description of this criterion) from screening until end of follow-up: <specify treatment, dose, unit, frequency, reason administered>.	Received a disallowed concomitant treatment	If classified as major protocol deviation, excluded from PP set.
44	Participant used disallowed inhibitor/medication (as defined in description of this criterion) from 1 month prior to screening until end of follow-up: <specify treatment, dose, unit, frequency, reason administered>.	Received a disallowed concomitant treatment	If classified as major protocol deviation, excluded from PP set.
44.1	Participant used disallowed inhibitor/medication (as defined in description of this criterion) from 1 month prior to screening until end of follow-up: <specify treatment, dose, unit, frequency, reason administered>.	Received a disallowed concomitant treatment	If classified as major protocol deviation, excluded from PP set.
45	Participant used disallowed Ethinylestradiol-containing contraceptives from 1 week prior to baseline until 12 weeks after EOSI: <specify treatment, dose, unit, frequency, reason administered>.	Received a disallowed concomitant treatment	If classified as major protocol deviation, excluded from PP set.
46	Participant did not receive dose of study drug <specify the study medication JNJ-3989/JNJ-6379/ NA/ PegIFN- $\alpha$ 2a> within window <specify out of window duration>.	Received a disallowed concomitant treatment	If classified as major protocol deviation, excluded from PP set.
46.1	Participant did not receive dose of study drug <specify the study medication JNJ-3989/ NA/ PegIFN- $\alpha$ 2a> within window <specify out of window duration>.	Received a disallowed concomitant treatment	If classified as major protocol deviation, excluded from PP set.
47	Participant missed <specify number of doses> dose of study drug JNJ-3989 at <specify visit>.	Received wrong treatment or incorrect dose	If classified as major protocol deviation, excluded from PP set.
48	Participant missed JNJ-6379: more than 5 doses or 3 consecutive doses within a four week period <specify number of missed dose/consecutive dose> within <specify duration of missed dose>.	Received wrong treatment or incorrect dose	If classified as major protocol deviation, excluded from PP set.
48.1	Participant was administered (a) dose(s) of JNJ-6379 after approval of CTPA6.	Received wrong treatment or incorrect dose	If classified as major protocol deviation, excluded from PP set.
49	Participant missed NA treatment for more than 5 doses within a four week period. <specify number of missed dose> within <specify duration of missed dose>.	Received wrong treatment or incorrect dose	If classified as major protocol deviation, excluded from PP set.
50	Participant missed 2 or more PegIFN- $\alpha$ 2a doses <specify number of missed dose>.	Received wrong treatment or incorrect dose	If classified as major protocol deviation, excluded from PP set.
51	Participant received expired study medication <JNJ-3989/ JNJ-6379/ NA/ PegIFN- $\alpha$ 2a>.	Other	If classified as major protocol deviation, excluded from PP set.
52	Study treatment <JNJ-3989, JNJ-6379/ NA/ PegIFN- $\alpha$ 2a> was not <prepared/ handled/ stored> in line with intervention-specific pharmacy manual/ study site investigational product and procedures manual <specify the incorrect preparation/handling/storage conditions>.	Other	If classified as major protocol deviation, excluded from PP set.
52.1	Study treatment <JNJ-3989, NA/ PegIFN- $\alpha$ 2a> was not <prepared/ handled/ stored> in line with intervention-specific pharmacy manual/ study site investigational product and procedures manual <specify the incorrect preparation/handling/storage conditions>.	Other	If classified as major protocol deviation, excluded from PP set.
53	Participant has event of "signs of decreasing liver function" based on laboratory or clinical findings but did not start NA treatment.	Received wrong treatment or incorrect dose	If classified as major protocol deviation, excluded from PP set.

Sequence No.	Protocol Deviation Description (DVTERM)	Protocol Deviation Coded Term (DVDECOD)	Exclude from PP
53.1	Participant has event of "signs of decreasing liver function" based on laboratory or clinical findings or HBV DNA value of >1,000,000 IU/mL (irrespective of confirmation and/or ALT increase) but did not start NA treatment.	Received wrong treatment or incorrect dose	If classified as major protocol deviation, excluded from PP set.
54	Participant has confirmed HBeAg seroreversion but did not start NA treatment.	Received wrong treatment or incorrect dose	If classified as major protocol deviation, excluded from PP set.
55	Participant has a confirmed post-treatment increase in HBV DNA >2,000 IU/mL and ALT >5 x ULN over a period of at least 4 weeks, but did not start NA treatment.	Received wrong treatment or incorrect dose	If classified as major protocol deviation, excluded from PP set.
55.1	Participant has a confirmed post-treatment increase in HBV DNA >2,000 IU/mL and ALT >5 x ULN over a period of at least 4 weeks, but did not start NA treatment.	Received wrong treatment or incorrect dose	If classified as major protocol deviation, excluded from PP set.
56	Participant has a confirmed post-treatment increase in HBV DNA >20,000 IU/mL over a period of at least 4 weeks, but did not start NA treatment.	Received wrong treatment or incorrect dose	If classified as major protocol deviation, excluded from PP set.
57	Participant has received a Covid-19 vaccine on the same day as PegIFN- $\alpha$ 2a administration.	Other	If classified as major protocol deviation, excluded from PP set.
58	Patients met at least one criteria of discontinuation of study intervention but did not stop	Developed withdrawal criteria but not withdrawn	Yes
71	<Specify study specific procedure(s)> <was/were> conducted prior to signing an informed consent form.	Other	If classified as major protocol deviation, excluded from PP set.
72	<Specify screening procedure(s)> <was/were> not performed within <28 days or 42 days> before first study drug administration.	Other	If classified as major protocol deviation, excluded from PP set.
73	Screen failed Participant was rescreened without agreement with the sponsor.	Other	If classified as major protocol deviation, excluded from PP set.
74	Study <specify the visit which> procedure not done at scheduled Visits.	Other	If classified as major protocol deviation, excluded from PP set.
75	Efficacy evaluation <specify assessment> not done at scheduled Visits.	Other	If classified as major protocol deviation, excluded from PP set.
76	Study Visits <specify visit> not performed per protocol.	Other	If classified as major protocol deviation, excluded from PP set.
77	Potential confusion between cross-over sites participating in REEF-studies.	Other	If classified as major protocol deviation, excluded from PP set.
78	Site reported protocol deviation not specified elsewhere.	Other	If classified as major protocol deviation, excluded from PP set.
79	<Specify visit(s)>: <specify blood, serum or urine, e.g., PK Samples, PMBC Sample> sample were collected in error however not destroyed.	Other	If classified as major protocol deviation, excluded from PP set.
80	Study Visits <specify visit> not performed per protocol.	Other	If classified as major protocol deviation, excluded from PP set.

